### Medical Conditions

- [10] Fulfillment of the modified New York (mNY) criteria (van der Linden et al. 1984) with sacroiliitis defined radiographically, based on central reading: sacroiliitis grade  $\geq 2$  bilaterally or grades 3 to 4 unilaterally
- [11] Have a history of other systemic inflammatory diseases (such as but not limited to lupus, vasculitis, or RA), or other chronic pain conditions (such as but not limited to fibromyalgia) that might confound the evaluations of benefit from ixekizumab therapy.  
**Note:** Patients with psoriasis who have never received and do not require systemic treatment for psoriasis, such as but not limited to oral agents or biologic therapies, can be included provided these patients fulfill the study entry criteria.
- [12] Have active Crohn's disease (CD) or active ulcerative colitis (UC)  
**Note:** Patients may be enrolled if they have had a history of inflammatory bowel disease (IBD), including CD and UC, but have had no exacerbation for  $\geq 6$  months prior to baseline, and, if currently on treatment, must be on stable treatment for  $\geq 6$  months prior to baseline.
- [13] Have evidence of active anterior uveitis (an acute episode) within the last 4 weeks prior to baseline randomization  
**Note:** These patients may be rescreened only one time  $\geq 4$  weeks after resolution of acute symptoms.
- [14] Have current or a history of lymphoproliferative disease, or signs or symptoms of lymphoproliferative disease, within 5 years prior to baseline randomization; or have active or history of malignant disease within 5 years prior to baseline randomization
- [15] Have a history of fluid overload, myocardial infarction (MI), uncompensated heart failure, or evidence of new-onset ischemic heart disease or, in the opinion of the investigator, other serious cardiac disease, within 12 weeks prior to baseline randomization
- [16] Presence of significant uncontrolled cerebrocardiovascular events (for example, unstable angina, unstable arterial hypertension, moderate-to-severe heart failure [New York Heart Association class III/IV], or cerebrovascular accident) at screening that, in the opinion of the investigator, pose an unacceptable risk to the patient if participating in the study or of interfering with the interpretation of data

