- [34] Have received any parenteral glucocorticoid administered by intraarticular, intramuscular, or intravenous injection within 6 weeks prior to baseline randomization; or are planning to receive a parenteral injection of glucocorticosteroids during the Blinded Treatment Dosing Period (Period 2) of the study
- [35] Use of any opiate analgesic at average daily doses of >30 mg/day of morphine or its equivalent or use of variable doses of any opiate analgesic within 6 weeks prior to baseline randomization. Exception for patients with pain that may interfere with undergoing an MRI: patient may receive premedication of ≤30 mg of morphine or equivalent, on the day of the MRI, for significant pain as judged by the investigator.
- [36] Had a live vaccination within 12 weeks prior to baseline randomization, intend to have a live vaccination during the course of the study or within 12 weeks of completing treatment in this study, or have participated in a vaccine clinical study within 12 weeks prior to baseline randomization. Investigators must review the vaccination status of their patients and follow the local guidelines for adult vaccination with nonlive vaccines intended to prevent infectious disease prior to therapy.
- Note:** Killed/inactive or subunit vaccines are expected to be safe; however, their efficacy with concomitant ixekizumab treatment is unknown.
- [37] Had a vaccination with Bacillus Calmette-Guérin (BCG) within 12 months prior to baseline randomization or intend to have this vaccination with BCG during the course of the study or within 12 months of completing treatment in this study

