### Diagnosics Assessments

- [38] Have a body temperature  $\geq 38^{\circ}\text{C}$  ( $100.5^{\circ}\text{F}$ ) at baseline randomization
- Note:** These patients may be rescreened once  $\geq 4$  weeks after documented resolution of elevated temperature.
- [39] Have evidence or suspicion of active or latent TB (refer to Section 5.3 for rescreening and Section 8.4.6 for details on determining full TB exclusion criteria)

[40] Are positive for human immunodeficiency virus (HIV) serology; ie, positive for human immunodeficiency virus antibody (HIVAb)

[41] Have evidence of or test positive for hepatitis B virus (HBV) by testing positive for 1) HBV surface antigen (HBsAg+) OR 2) anti-hepatitis B core antibody positive (HBcAb+) and are HBV DNA positive

**Note:** Patients who are HBcAb+ and HBV DNA negative may be enrolled in the study. Patients who meet these criteria at screening will be identified by the central laboratory and monitored during the study as detailed in Section 8.4.10.2.

[42] Have evidence of or test positive for hepatitis C virus (HCV). A positive test for HCV is defined as: 1) positive for hepatitis C antibody (anti-HCV Ab) and 2) positive via a confirmatory test for HCV (for example, HCV-polymerase chain reaction).

[43] Have electrocardiogram (ECG) abnormalities that are considered clinically significant by the investigator and would pose an unacceptable risk to the patient if participating in the study

[44] Have contraindications to MRI (for example, claustrophobia, pacemakers, aneurysm clips, intraocular metallic fragments).

**Note:** For claustrophobia, premedication with benzodiazepine is allowed (investigator should assess for potential interactions with other concomitant medication(s) such as opiates).

**Laboratory tests are not to be repeated unless there is a technical error or clinical reason to believe a result may need to be retested, within the screening period.** Laboratory tests can be repeated a maximum of 1 time, and results must be received and reviewed by study site personnel prior to randomization. For eligibility, the most recent lab test results must not meet any of the following criteria:

[45] At screening, have a neutrophil count  $<1500$  cells/ $\mu\text{L}$  ( $<1.50 \times 10^3/\mu\text{L}$  or  $<1.50$  GI/L)

[46] At screening, have a lymphocyte count  $<800$  cells/ $\mu\text{L}$  ( $<0.80 \times 10^3/\mu\text{L}$  or  $<0.80$  GI/L)

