### 5.3. Screen Failures

Individuals who do not meet the criteria for participation in this study (screen failure) may be rescreened in the following circumstances: Patients who test positive for latent TB at screening may be rescreened following appropriate treatment as described in Section 8.4.6; patients who do not qualify at screening under Exclusion Criteria [13], [23], [38], or [52] may be rescreened one time,  $\geq 4$  weeks after documented resolution of symptoms or from time of blood donation.

The screening MRI must be completed  $\leq 30$  days prior to baseline randomization (Visit 2). After consultation with Lilly medical, patients may be rescreened if screening MRI of the SIJ was  $> 30$  days prior to baseline randomization.

If a patient is unable to complete all screening procedures within the screening period, the patient may be rescreened after consultation with Lilly medical.

When rescreening is performed, the individual must sign a new informed consent form (ICF) and will be assigned a new identification number. To ensure that all eligibility criteria are met, all screening procedures must be repeated unless previously conducted within timeframes specified in the Schedule of Activities ([Appendix 2](#)).

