**Clinical Laboratory Tests**

Abbreviations: Ab = antibody; DNA = deoxyribonucleic acid; HBV = hepatitis B virus; HCV = hepatitis C virus; IgA = immunoglobulin A; RNA = ribonucleic acid; RBC = red blood cells; SGOT = serum glutamic oxaloacetic transaminase; SGPT = serum glutamic pyruvic transaminase; T4 = thyroxine; WBC = white blood cells.

- a Unscheduled blood chemistry, hematology, and urinalysis panels may be performed at the discretion of the investigator.
- b Cockcroft-Gault calculation is used for the calculated creatinine clearance.
- c For the fasting lipid profile, patients are not to eat or drink anything except water for 12 hours prior to test. Fasting is not required for the Screening Visit.
- d Serum pregnancy test for all women <60 years of age who are still of childbearing potential at Visit 1; after Visit 1, urine pregnancy test performed locally for women of childbearing potential.
- e Women  $\geq 40$  and <60 years of age who have had a cessation of menses for  $\geq 12$  months will have an FSH test confirming nonchildbearing potential ( $\geq 40$  mIU/mL).
- f Test required at Visit 1 to determine eligibility of patient for the study.
- g HBV DNA testing will be done in those patients who HBcAb+ at any time
- h See exclusion criteria (Section 5.2) specific to Hepatitis C antibody. A confirmatory test for HCV will be performed if the patient is positive for HCV antibody.
- i In countries where the QuantiFERON®-TB Gold test or T-SPOT® is available, either test may be used instead of the PPD TB test. The QuantiFERON-TB Gold test may be performed locally or centrally; the T-SPOT must be performed locally.

---

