[8] Female patient of childbearing potential with positive pregnancy test; or did not use a reliable method of birth control, if applicable	Do not exclude from PPS	Monitor and Stats
[10] Fulfillment of the mNY criteria with sacroiliitis defined radiographically, based on central reading	Exclude from PPS	Monitor and Stats
[11] Have a history of other systemic inflammatory diseases or other chronic pain conditions that might confound the evaluations of benefit from ixekizumab therapy	Exclude from PPS	Monitor
[12] Have active Crohn's disease (CD) or active ulcerative colitis (UC) at screening	Do not exclude from PPS	Monitor and Stats
[13] Have evidence of active anterior uveitis (an acute episode) within the last 4 weeks prior to baseline randomization	Do not exclude from PPS	Monitor and Stats
[14] Have current or a history of lymphoproliferative disease, or signs or symptoms of lymphoproliferative disease; or have active or history of	Do not exclude from PPS	Monitor

Important Protocol Deviation Category/Subcategory/Study Specific	Action for PPS Analysis	Source to Identify Protocol Deviationa
malignant disease within 5 years prior to Visit 2		
[15] Have had fluid overload, MI or new onset ischemic heart disease, uncompensated heart failure, or other serious cardiac disease within 12 weeks prior to Visit 2	Do not exclude from PPS	Monitor
[16] Presence of significant, uncontrolled cerebro-cardiovascular events at screening	Do not exclude from PPS	Monitor
[17] Presence of respiratory, hepatic, renal, gastrointestinal, endocrine, hematologic disorder at screening that pose unacceptable risk to patient or with interpretation of data	Do not exclude from PPS	Monitor
[18] Presence of neurologic or neuropsychiatric disorders at screening that pose unacceptable risk to patient or with interpretation of data	Do not exclude from PPS	Monitor
[19] Presence of significant uncontrolled neuropsychiatric disorder, recent history (30 days prior to V1 and anytime between V1 and V2) of a suicide attempt, have a score of 3 on Item 12 (Thoughts of Death or Suicide) of the QIDS-SR16 at Visit 1 or Visit 2, or at risk for suicide	Do not exclude from PPS	Monitor and Stats

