[35] Use of any opiate analgesic at average daily doses >30 mg/day of morphine or its equivalent or use of variable doses of any opiate analgesic within 6 weeks prior to baseline randomization. For Japan patients, use of pregabalin >300 mg/day or use of variable doses of pregabalin within 2 weeks prior to baseline randomization.	Exclude from PPS if: 1. Doses >30 mg/day any time within 6 weeks before randomization; or 2. Stopped or decreased dose for a current one <7 days before randomization; or 3. Started new treatment or increased dose for current one or started a new one <6 wks before randomization	Monitor and Stats
[36] Had a live vaccination or participated in a vaccine clinical study within 12 weeks prior to Visit 2, or intend to have a live vaccination during the study or within 12 weeks of completing study treatment	Do not exclude from PPS	Monitor
[37] Had a vaccination with BCG within 12 months prior to Visit 2, or intend to have this vaccination with BCG during the study or within 12 months of completing study treatment	Do not exclude from PPS	Monitor and Stats
[38] Have a body temperature $\geq 38^{\circ}\text{C}$ (100.5°F) at Visit 2	Do not exclude from PPS	Monitor and Stats
[39] Have evidence or suspicion of active or latent TB	Do not exclude from PPS	Monitor
[40] Are positive for human immunodeficiency virus serology (HIV)	Do not exclude from PPS	Monitor and Stats

Important Protocol Deviation Category/Subcategory/Study Specific	Action for PPS Analysis	Source to Identify Protocol Deviation a
[41] Have evidence of or test positive for hepatitis B virus (HBV) and are HBV DNA positive	Do not exclude from PPS	Monitor and Stats
[42] Have evidence of or test positive for hepatitis C virus (HCV)	Do not exclude from PPS	Monitor and Stats
[43] Have ECG abnormalities that are considered clinically significant and would pose an unacceptable risk to the patient if participating in the study	Do not exclude from PPS	Monitor
[44] Patients having contraindications to MRI	Do not exclude from PPS	Monitor
[45] At Visit 1, have a neutrophil count <1.50 GI/L	Do not exclude from PPS	Monitor and Stats
[46] At Visit 1, have a lymphocyte count <0.80 GI/L; for Japan patients, lymphocyte count <1.0 GI/L	Do not exclude from PPS	Monitor and Stats
[47] At Visit 1, have a platelet count <100 GI/L	Do not exclude from PPS	Monitor and Stats

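### SAP Table RHBX.6.12 row [35] omits the protocol's MRI-premedication exception, so its literal use would drop protocol-compliant patients from both per-protocol sets; rows [41] and [12] are also worded more narrowly than the protocol criteria

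*SAP*

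**What the plan says.** **Row [35], opiates.** Protocol Section 5.2, criterion [35], bars an average opiate dose above 30 mg/day of morphine-equivalent, or varying opiate doses, in the 6 weeks before randomisation. It then makes an exception for pain that could interfere with the scan: the "patient may receive premedication of ≤30 mg of morphine or equivalent, on the day of the MRI". Protocol Section 6.8.1 gives the same permission from Week 0 to Week 16. On timing, Protocol Section 5.3 states "The screening MRI must be completed" no more than 30 days before randomisation. Appendix 2 (footnote ee) repeats that limit, and Section 5.4 applies it to patients coming from Study RHBV.

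The SAP row repeats the dose and variability limits but not the exception. It lists three conditions for exclusion from the PPS:

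1. a dose above 30 mg/day at any time in the 6 weeks;
2. a stop or decrease less than 7 days before randomisation;
3. "Started new treatment or increased dose for current one or started a new one <6 wks before randomization".

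**Row [41], hepatitis B.** The protocol excludes patients "testing positive for 1) HBV surface antigen (HBsAg+) OR 2) anti-hepatitis B core antibody positive (HBcAb", the second route applying only where HBV DNA is also positive. The SAP row reads "Have evidence of or test positive for hepatitis B virus (HBV) and are HBV DNA positive". Protocol Appendix 3, footnote g, says "HBV DNA testing will be done in those patients who HBcAb+ at any time".

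**Row [12], inflammatory bowel disease (IBD).** The protocol Note admits patients with a history of IBD "but have had no exacerbation for" at least 6 months before baseline and, if treated, on stable treatment for as long. The SAP row covers only active Crohn's disease "or active ulcerative colitis (UC) at screening".

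Row [35] leads to exclusion from the PPS. Rows [41] and [12] are marked as not leading to exclusion. All three are identified by both monitors and statistical programming, and footnote a to the table says a deviation is shown if either source finds it.

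**The concern.** SAP Section 6.10.3 uses the PPS to support the primary ASAS40 result, with PPS-16 for Week 16 and PPS-52 for Week 52. A per-protocol set should lose patients who departed from the protocol. Row [35] as worded can also lose patients who followed it, because the action it permits (a new or extra opiate dose for the scan) is what condition 3 describes. An eligibility flag is fixed before randomisation, so it would remove the patient from both sets. Those removed would be patients with enough pain to need help through an MRI, in a trial whose primary endpoint includes spinal pain.

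The stakes for rows [41] and [12] are smaller. If the row wording becomes the programmed check, the important-deviation table could leave out some patients whom the protocol bars. IBD is an adverse event of special interest (Protocol Section 8.2.2), so entry deviations of that kind should be reported completely.

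**Working it through.** **Background: the plan's own figure.** For 46% versus 18% with 100 per group and a two-sided Fisher's exact test at 0.05, exact enumeration gives 98.8% power. This agrees with the stated figure of about 98%. The finding does not depend on it.

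**Row [35]: does the screening MRI always fall inside the window?**

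- SAP window: 6 weeks × 7 = 42 days.
- Earliest permitted screening MRI: 30 days before randomisation.
- Margin: 42 − 30 = 12 days.

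Every in-window screening MRI therefore lies inside the opiate window with at least 12 days to spare.

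**Which conditions would a permitted dose meet, read literally?**

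- *Patient not otherwise on opiates.* Condition 3 is met as a new start. Condition 2 could also be met if the scan is less than 7 days before randomisation. Condition 1 is not met, since a permitted dose is at most 30 mg.
- *Patient on a stable opiate dose.* Condition 3 is met as an increase. Condition 1 is met on the day if the full 30 mg is added to any regular dose. Averaged over the window, the premedication adds only 30/42 ≈ 0.7 mg/day. Condition 1 works on any day, whereas the protocol limit is an average, so the two can disagree.

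**How large could this be?** The documents give no usage figure. Purely as an assumption, 2% to 10% of 300 would be 6 to 30 patients. Removing 5 or 10 per arm changes exact Fisher power for 46% versus 18% as follows:

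| Patients per arm | Power |
|---|---|
| 100 | 98.8% |
| 95 | 98.4% |
| 90 | 97.8% |

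The problem is who is in the PPS, not lost power.

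**Row [41]: protocol and SAP wording side by side.** Here the SAP's HBV positivity is taken to mean HBsAg+ or HBcAb+.

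| HBsAg | HBcAb | HBV DNA | Protocol excludes | SAP row met |
|---|---|---|---|---|
| + | − | negative or not tested | yes | no |
| + | + | negative or not tested | yes | no |

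All other combinations agree, and no mismatch runs the other way. An HBsAg+/HBcAb− patient has no planned DNA test under Appendix 3, footnote g.

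**Row [12].** A patient whose disease is quiet at screening, but who had an exacerbation or a treatment change within 6 months of baseline, fails the protocol Note and does not meet the SAP row. The same holds for a flare between screening and baseline.

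**The case against.** The strongest defence of row [35] is that it works in two steps. The first column defines the deviation, and the second says which deviations lead to exclusion. The PPS removes patients with important protocol deviations, and a dose the protocol permits is not a deviation. In a patient not on opiates, one permitted dose is not an average above 30 mg/day, and whether it counts as varying doses is arguable. The SAP's Revision History also says that programming guidance was moved to an external document, which may contain the exception. And PPS conditions need not copy eligibility: rows [27] to [29] set cut-offs of their own.

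Part of this stands. A reader might infer that every premedicated patient will be excluded. The documents do not establish that, because it requires condition 3 to be applied literally and the programming specification is not available. But the defence does not remove the problem. The protocol placed the exception inside this criterion, which suggests such a dose would otherwise count. The SAP is the prespecified rule and states no exception. Under the either-source rule, a programmed flag stands even if the monitor sees no deviation.

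For rows [41] and [12], a reader might infer that the affected patients can never be flagged. That is not supported either. A monitor working from the protocol can list them, and one source is enough. The rows may also be shortened labels for the numbered criteria.

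Finally, a reader might infer a biased treatment comparison. Premedication for the screening MRI precedes randomisation, so its use cannot depend on the assigned arm. Removing those patients changes who is represented in the PPS but does not by itself favour an arm.

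**Conclusion.** The mismatch in row [35] is real. The SAP omits an exception the protocol grants, and its window always covers the screening MRI (30 days against 42). Applied literally, condition 3 would exclude protocol-compliant patients from PPS-16 and PPS-52. This conclusion rests on that literal application and on the external specification not already containing the exception.

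The number affected is unknown; the 2% to 10% range is illustrative only. The ITT primary analysis, the alpha allocation and the stated power do not change, and the PPS analysis is supportive.

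Rows [41] and [12] are a secondary point. Their wording, and any programmed check built on it, is narrower than the protocol criteria. The effect is confined to the important-deviation table and listing, and is incomplete reporting only if the monitors do not also pick up the patients concerned.

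**What to change.** - **Row [35]:** carry over the exception from protocol criterion [35] in the protocol's own terms ("patient may receive premedication of ≤30 mg of morphine or equivalent, on the day of the MRI") and state that such use is disregarded in conditions 1 to 3. Do not add a restriction, such as one dose only, that the protocol does not contain.
- **Row [41]:** reconcile with protocol criterion [41], under which HBsAg positivity alone suffices and HBV DNA positivity is required only on the HBcAb+ route.
- **Row [12]:** reconcile with the Note to protocol criterion [12], including its 6-month conditions on exacerbation and stable treatment before baseline.
- **Programming:** check that the external specification matches the amended rows. Footnote a to the table still refers to a programming-guidance column that is no longer there, and can be corrected at the same time.

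The cost is three table entries and the matching specification check. No clinical rule changes and no patient data are needed beyond what is already collected.

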### **9.2.3. Analysis Populations**

The following analysis populations will be used; additional analysis populations will be specified in the SAP:

**Intent-to-Treat Population (ITT):** Unless otherwise specified, efficacy and health outcomes analyses for Period 2 (Blinded Treatment Dosing Period) will be conducted on the ITT population, defined as all randomized patients, even if the patient does not take the assigned treatment, does not receive the correct treatment, or otherwise does not follow the protocol. Patients will be analyzed according to the treatment to which they were assigned.

**Per-Protocol Set (PPS):** In addition, the primary efficacy analysis will be repeated using the PPS, which is defined as all randomized patients who are compliant with therapy, who do not have significant protocol deviations, and whose investigator site does not have significant GCP issues that require a report to the regulatory agencies prior to Week 52 (Visit 15). Compliance with therapy is defined to be missing no more than 20% of expected doses, not missing 2 consecutive doses (all injections at a visit is counted as 1 dose), and not have any occurrence of double-dosing (that is, took more injections at the same time point than specified in the protocol) during Period 2 (Blinded Treatment Dosing Period). For patients who are deemed as inadequate responders by investigators after Week 16 and for whom the investigator indicates the need for modified treatment by the use of rescue ixekizumab 80 mg Q2W, the requirements for PPS only apply during the treatment period prior to the assignment of modified treatment by ixekizumab 80 mg Q2W.

Significant protocol deviations will be described in the SAP. Patients will be analyzed according to the treatment to which they were assigned.

**Safety Population:** Safety analyses for Period 2 will be conducted on the safety population, defined as all randomized patients who received at least 1 dose of study treatment. Patients will be analyzed according to the treatment to which they were assigned in that period.

**Follow-up Population:** Safety analyses for Period 3 (Post-Study Follow-Up Period) will be conducted on the follow-up population, defined as all randomized patients who received at least 1 dose of study treatment and have entered the Post-Study Follow-Up Period. Patients will be analyzed according to the treatment they received before entering the follow-up period.

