#### 6.1.1. Analysis Populations

The following major analysis populations will be used (additional analysis populations for specific analysis will be defined in the corresponding analysis section):

**Intent-to-Treat Population (ITT Population):** Unless otherwise specified, efficacy and health outcomes analyses for Period 2 will be conducted on the ITT Population, defined as all randomized patients, even if the patient does not take the assigned treatment, does not receive the correct treatment, or otherwise does not follow the protocol. Patients will be analyzed according to the treatment to which they were assigned at Week 0. For patients who were deemed as inadequate responders by their investigators and were treated with biologic rescue of ixekizumab 80 mg Q2W, only data up to the time of initiation of biologic rescue of ixekizumab 80 mg Q2W will be included in the primary analyses for Period 2.

**Per-Protocol Set (PPS):** The primary efficacy analysis will be repeated using the PPS, which is defined as all randomized patients who do not have a subset of important protocol deviations that

impact the primary efficacy endpoint (Section 6.16). For example, patients who are not compliant with therapy during Period 2 will be excluded from the PPS. Compliance with therapy is defined to be missing no more than 20% of expected doses, not missing 2 consecutive doses (all injections at an injection week are counted as 1 dose), and not have any occurrence of over-dosing (that is, took more injections at the same time point than specified in the protocol). For sensitivity analyses for primary endpoint of ASAS40 at Weeks 16 and 52, two PPS's will be defined: PPS-16 requires that important protocol deviations not be occurring during Weeks 0 to 16; while PPS-52 requires important protocol deviations not be occurring during Weeks 0 to 52 when patients were on originally assigned treatment.

Patients will be analyzed according to the treatment to which they were assigned.

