Missing ASAS components for ASAS40 derivation: not having Week 16 measurement for patients who have completed week 16	Do not exclude from PPS. Note: if missing ASAS components lead to missing ASAS40, such patient will be treated as non-responder for the Week 16 ITT analyses	Stats
Had unqualified site personnel perform clinical safety and/or efficacy assessments	Do not exclude from PPS	Monitor
Category: Investigational Product		
Subcategory: Treatment Assignment/Randomization Error		
Took incorrect study medication	Do not exclude from PPS. Analyze 'As randomized' or 'As assigned'.	Stats and monitor
Subcategory: Compliance		
	Exclude from PPS when occurred during Period 2 prior to use of rescue ixekizumab 80 mg Q2W	Stats

Important Protocol Deviation Category/Subcategory/Study Specific	Action for PPS Analysis	Source to Identify Protocol Deviationa
Subcategory: Patient took medication not fit for use		
	Do not exclude from PPS	Monitor
Subcategory: Unblinding		
	Exclude from PPS	Monitor
Subcategory: Other		
Randomized but did not take any study medication	Exclude from PPS	Stats
Category: Safety		
Subcategory: SAEs		
SAE not reported within designated timeline	Do not Exclude from PPS	Monitor
Category: Informed Consent		
Subcategory: Informed Consent not Obtained/Missing/Lateb		
	Exclude from PPS	Monitor
Subcategory: Improper Consent		
	Do not Exclude from PPS	Monitor
Category: administrative/oversight		
Subcategory: Reg/Ethic Approvals		
	Exclude from PPS	Monitor
Subcategory: Other		
Enrolled in a site with significant GCP non-compliance issue	Exclude from PPS	Monitor

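### The per-protocol set keeps patients who took the wrong study medication, however many doses were wrong, and the compliance rule does not catch them

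*SAP*

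**What the plan says.** SAP Section 6.1.1 defines the PPS as "all randomized patients who do not have a subset of important protocol deviations", the subset being those that bear on the primary efficacy endpoint. Protocol Appendix 1 describes the set as patients who followed the protocol well enough for their data to show what the treatment does.

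Table RHBX.6.12 in SAP Section 6.16 gives the action for each deviation. For "Took incorrect study medication", under treatment assignment or randomization error, the action is "Do not exclude from PPS. Analyze 'As randomized' or 'As assigned". No number or duration of wrong doses is attached.

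The compliance row, which follows directly, reads "Exclude from PPS when occurred during Period 2 prior to use of rescue ixekizumab 80 mg Q2W". SAP Section 6.1.1 agrees: "patients who are not compliant with therapy during Period 2 will be excluded from the PPS". Compliance has three limbs: "missing no more than 20% of expected doses", no two consecutive doses missed, and "not have any occurrence of over-dosing (that is, took more injections at the same time point than specified in the protocol". Protocol Section 9.2.3 has the same third limb: "not have any occurrence of double-dosing (that is, took more injections at the same time point than specified in the protocol". Further down, the table excludes patients who were randomized but never took study medication.

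SAP Section 6.8 computes compliance as injections administered over injections prescribed. The numerator comes from the case report form question on whether the dose was given.

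**The concern.** The ITT population already includes patients who receive the wrong treatment, analysed as assigned. A per-protocol analysis adds information only if it leaves out patients whose treatment departed materially from the assigned one. Here the departure most directly tied to treatment received is kept, while lesser ones exclude. A placebo patient who was given ixekizumab for much of Period 2 would count in the placebo arm of the PPS, and the reverse. What is at stake is the value of the PPS analyses of ASAS40 at Weeks 16 and 52 as a check on the primary result. The primary result itself is not at stake.

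**Working it through.** **Does any other rule remove these patients?** Take a patient who completes Period 2 and receives every injection on schedule, all of the wrong product.

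- Prescribed injections (SAP Section 6.8): 2 at Week 0 plus 25 from Week 2 to Week 50 = 27, on 26 dosing occasions. This reproduces the SAP's figure of 27.
- Compliance = 27/27 = 100%. Nothing is missed, and no time point has a surplus injection, so all three limbs are met.
- The row for patients who took no study medication does not apply. The unblinding row or another excluding row might apply, but only for a separate reason.

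So, as written, the patient stays in PPS-16 and PPS-52 under the assigned arm.

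**How the rules compare**

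| Departure | Action |
|---|---|
| Up to 5 non-consecutive missed doses (20% of 26 = 5.2) | Kept |
| Two consecutive missed doses | Excluded |
| One surplus injection at one time point, before rescue (28/27 = 103.7%) | Excluded |
| No study medication taken | Excluded |
| Wrong product for any number of doses | Kept |

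**Size, for placebo/Q2W crossovers only.** The inputs are the Week 16 planning rates in SAP Section 5.2: 46% for Q2W and 18% for placebo, 100 per arm, two-sided Fisher's exact test at 0.05. Exact power at these inputs is 98.8%, against the plan's approximate 98%.

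- One fully crossed patient shifts an arm of 100 by (0.46 − 0.18)/100 = 0.28 percentage points toward the other arm.
- If a share f of both arms took the other arm's product throughout, the Q2W rate is 0.46(1 − f) + 0.18f and the placebo rate is 0.18(1 − f) + 0.46f. The difference is therefore 0.28(1 − 2f).

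The documents give no rate of wrong medication, so f is an assumption. The PPS is held at 100 per arm for illustration.

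| f | Difference (points) | Exact Fisher power |
|---|---|---|
| 0 | 28.0 | 98.8% |
| 1% | 27.4 | 98.4% |
| 2% | 26.9 | 98.0% |
| 5% | 25.2 | 96.3% |

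The documents state no planning rate for Q4W, so the calculation cannot be extended to that comparison.

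**The case against.** The best defence is that this is an open, pre-specified choice. Protocol Section 9.2.3 leaves the description of significant deviations to the SAP and itself analyses PPS patients as assigned. A reader might infer that the SAP contradicts the protocol, or that the as-assigned label is the error. The documents support neither. The weakness is that the patients are kept, not how they are labelled.

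A reader might also infer that the bias always runs toward no difference. It need not. With three arms and two starting doses, incorrect medication can mean a Q4W/Q2W mix-up, and a Q4W patient given Q2W product receives more active drug. It can also mean a wrong starting dose, which leaves the patient in the same analysis group because groups are pooled over starting dose.

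The size shown is an upper illustration. It needs whole-course swaps, and the IWRS assignment with a package confirmation number (SAP Section 5.3) guards against those. The detailed programming rules sit outside the SAP, so we cannot see whether the row flags a single wrong kit or sustained wrong treatment.

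The contrast with over-dosing is also narrower than it may look. Only a surplus at the same time point excludes, and that rule comes from the protocol.

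Finally, excluding for any single wrong syringe would be stricter than the missed-dose rule. All of these limits stand. None of them explains why an unlimited number of wrong doses is acceptable in a per-protocol set.

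**Conclusion.** The point holds as an inconsistency within the PPS definition, and it is minor. The written rules keep a patient who never took the assigned product but took another arm's, and exclude a patient who took nothing. For placebo/active crossovers this dilutes the PPS comparison by 0.28 points per fully crossed patient per arm of 100, at the Week 16 planning rates. For other product errors the direction is open. The total effect depends on a rate the documents do not give and is probably small.

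It would be wrong to infer that the trial's conclusion is at risk. The primary analysis is ITT, the PPS analysis is supportive (SAP Section 6.10.3), and it appears in neither testing sequence in SAP Section 6.5. Dilution would make a superiority check more conservative; it would not create a false claim of benefit.

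**What to change.** Change the action in Table RHBX.6.12 so that a dose of incorrect product counts as a missed dose of the assigned treatment under the existing compliance rule. Exclude the patient when more than 20% of doses, or two consecutive doses, were wrong or missed: from PPS-16 over Weeks 0 to 16, and from PPS-52 up to Week 52 or rescue.

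For PPS-52 in a completer this tolerates up to 5 non-consecutive wrong or missed doses of 26. For PPS-16, the 8 dosing occasions from Week 0 to Week 14 give 20% of 8 = 1.6, so one such dose is tolerated. An isolated kit error would therefore not exclude anyone.

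The ITT analysis stays as randomized, and sample size, power and alpha do not change. The cost is one table cell and a matching line in the programming specification, and probably a few patients fewer in a supportive set. It does add a post-randomization exclusion, so it should be settled before the Week 52 unblinding. If the sponsor prefers to keep these patients, the SAP should say why, given that taking no medication or a single over-dose excludes.
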